6.4 Duration of Subject Participation

Each subject will receive rapastinel (GLYX-13) until rapastinel (GLYX-13) is approved for marketing by the U.S. FDA or until the subject discontinues from the study, or until the Sponsor stops the study.

7 SELECTION OF STUDY POPULATION

7.1 Inclusion Criteria

The subject must meet the following criteria to be eligible for enrollment into this study:

- 1. Participants who have completed 8 or more weeks of treatment in the preceding study (GLYX13-C-202, NCT01684163
- 2. Participants who wish to continue treatment with rapastinel (GLYX-13) after the preceding study
- 3. Meets Diagnostic and Statistical Manual, Fourth Edition, Text Revision (DSM-IV-TR) criteria for major depressive disorder (MDD)
- 4. Female subjects of childbearing potential with a negative serum pregnancy test prior to entry into the study and who are practicing an adequate method of birth control (eg oral or parenteral contraceptives, intrauterine device, barrier, abstinence) and who do not plan to become pregnant during the course of the study. Female subjects may be included without a negative serum pregnancy test if they are surgically sterile or at least 2 years postmenopausal.
- 5. Clinical laboratory values <2 times the upper limit of normal (ULN) or deemed not clinically significant per the investigator and medical monitor
- 6. Ability to understand the requirements of the study, provide written informed consent, abide by the study restrictions, and agree to return for the required assessments
- 7. Based on the investigator and medical monitor's clinical judgment, subjects with eating disorders, obsessive compulsive disorder (OCD), panic disorder, post-traumatic stress disorder (PTSD), and generalized anxiety disorders secondary to major depressive episodes (MDEs) are permitted.

7.2 Exclusion Criteria

The subject will not be eligible for enrollment if any of the following criteria are met:

- 1. Axis I diagnosis of delirium, dementia, dysthymia, amnestic or other cognitive disorder, schizophrenia or other psychotic disorder, bipolar I or II disorder, eating disorder (anorexia or bulimia nervosa), obsessive-compulsive disorder, panic disorder, acute stress disorder, agoraphobia, social phobia, attention-deficit hyperactivity disorder (ADHD), or PTSD
- 2. A clinically significant current Axis II diagnosis of borderline, antisocial, paranoid, schizoid, schizotypal, or histrionic personality disorder
- 3. Experiencing hallucinations, delusions, or any psychotic symptomatology in the current episode; lifetime history of psychosis

- 4. Huntington's, Parkinson's, Alzheimer's, Multiple Sclerosis, or a history of seizures or strokes
- 5. Currently hospitalized or residing in an in-patient facility during study participation
- 6. Substance abuse since the end of participation in GLYX13-C-202, including greater than or equal to 5 units of alcohol per day where 1 unit = ½ pint of beer, 1 glass of wine 4 oz, or 1 oz. of spirits consumed most weeks or in the opinion of the investigator
- 7. Women who are planning to become pregnant during the course of the study
- 8. Allergy or intolerance to current antidepressant or other current medications
- 9. Participation in any clinical trial of an investigational product or device within 30 days of enrollment in this trial with the exception of GLYX13-C-202.
- 10. Positive screen for drugs of abuse: cocaine, marijuana, PCP, ketamine, opioid or other agent that in the opinion of the investigator is being abused
- 11. Pose current (past 6 months) suicide risk based on administration of the C SSRS and the investigator's clinical judgment
- 12. Human immunodeficiency virus (HIV) infection (based on the based on the HIV-1 & HIV-2 antibody screen) or other ongoing infectious disease

7.2.1 Adequate methods of birth control

Over the course of the study, females of childbearing potential must practice a method of contraception with greater than 90% reliability. Women of childbearing potential are women who are not 2 years postmenopausal, or not surgically sterile. Typical acceptable forms of birth control are:

- cervical cap with spermicide
- diaphragm with spermicide
- male condom
- oral contraceptives
- intrauterine devices
- medroxyprogesterone acetate
- levonorgestrel subdermal implants
- abstinence

7.2.2 Permitted Concomitant Treatment

Subjects may use any drug not specifically excluded in the exclusion criteria.

[figure not shown]
During the study, subjects will be reminded to abstain from alcohol and not to use illegal drugs or prescription drugs not prescribed by a doctor.

Cough syrup with dextromethorphan cannot be used within 2 weeks before the baseline visit and cannot be used during the study.

7.2.3 Recording of Prior/Concomitant Therapy

All antidepressant drugs and other drugs taken during the current depressive episode to within 30 days of Screening will be carefully documented. During the study, subjects will report permitted concomitant drugs taken to the site study personnel during each study visit.

8 STUDY DRUGS

8.1 Study Drug Storage Conditions

Study drug must be stored refrigerated

Drug supplies will be kept in an appropriate secure area and stored in accordance with specifications on the drug labels. Site will maintain shipment records from the depot and ensure supplies are received under the proper conditions. A drug inventory record of supplied, received, dispensed, and returned study drug must be maintained by the pharmacy representative on an ongoing basis. The investigator is required to return unopened kits of study drug to the Sponsor at the end of the trial (Sponsor will provide specific instructions). The pharmacy representative is required to maintain copies of study drug shipping receipts, drug accountability records, and records of return or final disposal of study drug. This form must be available at all times for inspection by the medical monitor or field monitor.

8.2 Method of Assigning Subjects to Treatment Groups

Subjects will be assigned initially to the dose level and frequency to which they were assigned during the randomized withdrawal portion of clinical study GLYX13-C-202. Following one month of participation, dose level and dose frequency may be changed by the investigator according to a treatment plan formulated by the investigator at the investigator's discretion.

8.3 Study Drug Dosing

Study drug will only be administered to eligible subjects under the supervision of the investigator or identified subinvestigator(s) or other assigned personnel licensed to administer IV drugs.

Table 2 Dose Volumes for Dosing

Dose Level mg IV	Dose Volume (mL/subject)	This replaces
225	3.0	5 mg/kg
450	3.0	10 mg/kg

Study drug (rapastinel [GLYX-13]) will be administered using a syringe attached to a butterfly catheter in a "slow bolus" to an upper extremity vein to each study subject within approximately 1 to 2 minutes.

8.3.1 Blinding

This is an open label safety study.

8.4 Dose Interval

Dose interval for the first month of participation will be that (weekly or biweekly) to which the subject was assigned during the randomized withdrawal phase of GLYX13-C-202. The investigator will then formulate a treatment plan in which dose interval will remain the same or change. The treatment plan may be modified from time to time by the investigator if it is deemed prudent based on subject's depression status.

8.5 Receipt of Supplies

Upon receipt of the investigational drug, the pharmacist or designee will visually inspect the shipment and verify the drug information, quantity, and condition of the study drug received. The pharmacist will complete the accompanying Temptale form by following the instructions on the form.

The study drug will be supplied in kits, each containing 1 prefilled syringe, a plunger, and a needle, and labeled with the protocol number, kit number, contents, lot number, storage information, Sponsor, warning language ("Caution: New Drug—Limited by Federal Law to Investigational Use. Keep Out of Reach of Children"), and instructions for use to refer to protocol, as well as fields for the patient identification (PID) number, patient initials, study center number, visit number, and date dispensed to be recorded. The study center will write on both panels the patient's PID number and patient's initials along with the study center number, visit number, and date dispensed.

The study center personnel will complete the kit label and attach the tear-off portion to the source documents.

The prefilled syringe will be labeled with the protocol number and kit number. The study center personnel will write the PID number on the prefilled syringe associated with the kit mentioned above. The prefilled syringe will not have a tear off and will remain on the prefilled syringe.

8.6 Study Drug Accountability

The Sponsor will provide the investigator with sufficient amounts of the study drug to begin the study. It is the responsibility of the investigator to ensure that a current record of inventory/study drug accountability is maintained. Inventory records must be readily available for inspection by the study monitor during the study and are open to inspection by regulatory authorities at any time.

Pharmacy personnel or other designated site staff will account for, store and dispense the study drug. At the end of the study, all study drug must be accounted for. In addition, at the end of the study, all unused study drug should be returned to the Sponsor or the local distributor at the address provided in the SSARF (Study Specific Accountability Return Form).

8.7 Study Drug Handling and Return

The study drug must be stored refrigerated

. Sites must report any temperature excursions as described in the Study Reference Manual or contact the Sponsor or its designee for further instructions.

[figure not shown]
Upon completion or termination of the study, all unused kits of study drug will be returned to the Sponsor's representative. The site will dispose of any used study drug as part of the site internal SOP for disposing of sharps and biohazard material. Instructions for return of unused study drug will be supplied near completion of the study.

[figure not shown]
9 STUDY ASSESSMENTS AND PROCEDURES

[figure not shown]
9.1 Standardization of Data Capture

Dosing of study drug to subjects in this study will be performed by a qualified designee under the supervision of a licensed health care provider listed on the FDA Form 1572. Accurate, consistent, and reliable data will be ensured by using standard practices and procedures presented by the sponsor and applicable regulatory authorities.

9.2.7 Total Blood Collection Volume

The total volume of blood collected over each year of participation will be less than 100 mL.

10 SUBJECT AND STUDY DISCONTINUATION

10.1 Screen Failures

Subjects who sign and date the informed consent form (ICF) but who fail to meet the inclusion and exclusion criteria are considered screen failures. A screening log, which documents the subject initials and reason(s) for screen failure, is to be maintained by the investigator for all screen failures. A copy of the log should be retained in the investigator's study files. Subjects may be rescreened on a case-by-case basis upon discussion between the investigator and the Medical Monitor.

10.2 Discontinuation from Study

A subject may be prematurely discontinued from the study for any of the following reasons:

- Adverse event
- Withdrew consent
- Physician decision
- Pregnancy
- Protocol deviation
- Lost to follow-up
- Site terminated by Sponsor
- Study terminated by Sponsor
- Other

[figure not shown]
10.3 Site Discontinuation

Reasons for discontinuation of the study may include, but are not limited to, the following:

- The incidence or severity of AEs in this or other studies indicates a potential health hazard to subjects.
- Subject enrollment is unsatisfactory.
- Investigator request to withdraw from participation.
- Sponsor decision.
- Serious and/or persistent non-compliance by the investigator with the protocol, the clinical research agreement, the Form FDA 1572 or applicable regulatory guidelines in conducting the study.
- Institutional review board (IRB) decision to terminate or suspend approval for the investigation or the investigator.
- Investigator fraud (altered data, omitted data, or manufactured data).

11 EFFICACY ASSESSMENTS

12.7 Adverse Events

Subjects should be queried in a non-leading manner, without specific prompting (eg, "How are you feeling?"). The site study staff should assess emerging symptoms of dissociative reaction similar to those caused by other NMDA antagonists including memory impairment, disturbance in time, body or environmental perception, stilted speech, emotional withdrawal, impaired coordination, motor retardation, bizarre reasoning or illusory experiences in any sensory perception, or confused state; such symptoms may be captured as adverse events.

An "adverse event" is any untoward, undesired, unplanned clinical event in the form of signs, symptoms, disease, or laboratory or physiological observations occurring in a human being participating in a clinical study with an investigational product, regardless of causal relationship. A "pre-existing" condition is one that is present before study drug dosing and is reported as part of the subject's medical history. Pre-existing conditions should be reported as an AE only if the frequency, intensity, or character of the pre-existing condition worsens during the course of the study.

Laboratory abnormalities are not considered AEs unless they are associated with clinical signs or symptoms, or require medical intervention. However, a laboratory abnormality (eg, a clinically significant change detected on clinical chemistry, coagulation, hematology, urinalysis) that is independent from the underlying medical condition and that requires medical or surgical intervention, or leads to study drug interruption or discontinuation, must be considered an AE.

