5 STUDY OBJECTIVES

5.1 Primary Objective

The primary objective of this study is to examine the safety of long term repeat exposure to rapastinel (GLYX-13) in subjects who participated in GLYX13-C-202.

The primary endpoint of this study is to examine the number of participants who experience an adverse event over the course of the study.

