12.7.1 Recording of Adverse Events

Subjects should be instructed to report all AEs to the investigator. AE collection begins at signing of ICF and ends 30 days after last dosing injection. In addition, the investigator should seek to elicit any clinical or objective reactions by specific questioning (eg, "How have you been feeling?") and, as appropriate, by examination. Information on all AEs should be recorded on the eCRF. All clearly related signs, symptoms, and results of diagnostic procedures performed because of an AE should be grouped together and recorded as a single diagnosis. The component parts of the diagnosis may be listed for verification. If the AE is a laboratory abnormality that is part of a clinical condition or syndrome, it should be recorded as the syndrome or diagnosis rather than the individual laboratory abnormality.

To avoid vague, ambiguous, or colloquial expressions, all AEs should be recorded in standard medical terminology on the eCRF and on the medical record rather than in the subject's own words. Each AE will also be described in terms of duration (start and stop date), severity, association with the study drug, action(s) taken, and outcome.

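### Protocol 12.7 makes recording of assessed dissociative symptoms permissive, at odds with its own adverse event definition and the record-all rule in 12.7.1

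*Protocol*

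**What the plan says.** Protocol section 12.7 opens with the way subjects are to be asked: "Subjects should be queried in a non-leading manner, without specific prompting". It then gives a separate duty: "The site study staff should assess emerging symptoms of dissociative reaction similar to those caused by other NMDA antagonists". A list follows, including memory impairment, altered perception, impaired coordination and confusion, and the sentence ends "such symptoms may be captured as adverse events".

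The next paragraph says that an adverse event "is any untoward, undesired, unplanned clinical event in the form of signs, symptoms, disease, or laboratory or physiological observations", and that this applies "regardless of causal relationship". A condition present before dosing counts only if it worsens. Section 12.7.1 adds the recording rule: "Information on all AEs should be recorded on the eCRF". It also asks that clearly related signs and symptoms be entered as one diagnosis.

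Section 5.1 states the primary endpoint, which is to "examine the number of participants who experience an adverse event over the course of the study". SAP section 9.0 names the safety parameters as adverse events, laboratory values, vital signs and ECG. SAP section 9.1 tabulates treatment-emergent events by system organ class and preferred term.

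**The concern.** Assessment of these symptoms is directed, but recording a positive finding is worded as a choice, and the visible text gives no criterion for when a symptom may be left out. For these symptoms the specific instruction is weaker than the general one.

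Any error goes one way, because permissive recording can lower a count but cannot raise it. The study has no control arm to put a low count in context. The SAP's adverse event tables are not broken down by site, so uneven recording across the 10 planned sites would not show.

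The symptoms bear on the drug's rationale. The protocol Introduction says that psychotomimetic effects make ketamine and CP-101,606 impractical for chronic use, and reports none on the BPRS+ in GLYX13-C-201 after a single dose of rapastinel. The present study is about long-term repeat exposure. Among the safety parameters visible in the SAP, only adverse event records would show these symptoms.

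**Working it through.** **Text check.** The plan gives no figure to reproduce: there is no assumed event rate, no power calculation and no inferential analysis. The main check sets the rules side by side.

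1. The definition in 12.7 covers symptoms and has no causality filter, so a new untoward dissociative symptom is an adverse event.
2. Section 12.7.1 then calls for it to be recorded.
3. The sentence on dissociative symptoms says only that it *may* be captured. Rules 1 and 2 leave no room for that choice.
4. Section 12.7 narrows the general definition in two other places, for laboratory abnormalities and for pre-existing conditions. A site could take the permissive sentence as a third exception.
5. For some laboratory abnormalities the same section uses mandatory language. It does not do so here.
6. Short duration is no reason for omission, since Grade 1 in section 12.7.2 expressly includes transient discomfort.

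**Illustration of size.** N = 100 is the upper limit in protocol section 14.4. Three further inputs are assumptions, because the documents give none:

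- d: share of subjects with a dissociative symptom
- o: share with some other adverse event, taken as independent of d
- c: share of affected subjects for whom at least one such symptom is recorded

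Subjects with a recorded dissociative event = N × d × c. With d = 10%, full recording gives 100 × 0.10 × 1 = 10 and half recording gives 100 × 0.10 × 0.5 = 5.

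Primary count = N × [1 − (1 − o)(1 − d × c)]. The loss against full recording is N × (1 − o) × d × (1 − c).

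| o | Primary count, c = 100% | Primary count, c = 50% | Loss |
|---|---|---|---|
| 50% | 55.0 | 52.5 | 100 × 0.50 × 0.10 × 0.5 = 2.5 |
| 80% | 82.0 | 81.0 | 100 × 0.20 × 0.10 × 0.5 = 1.0 |
| 90% | 91.0 | 90.5 | 100 × 0.10 × 0.10 × 0.5 = 0.5 |

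The extreme case is no recording at all (c = 0). Over d from 5% to 30% and o from 50% to 95%, the primary loss runs from 100 × 0.05 × 0.05 = 0.25 to 100 × 0.50 × 0.30 = 15 subjects.

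**Effect on a table.** SAP section 9.1 has a table of events in at least 2% of subjects, which is 2 subjects at N = 100. Suppose 3 subjects have the same preferred term and each is recorded independently with probability 50%. The chance that at most 1 is recorded, so that the term drops out, is 1/8 + 3/8 = 50%.

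**The case against.** The strongest reply is that the plan already requires these records. Read together, the definition in 12.7 and the record-all rule in 12.7.1 cover any new untoward symptom, and a site that sees one and does not enter it departs from 12.7.1. This stands as the harmonised reading. A reader might infer that the protocol hands sites free discretion over the primary endpoint. The documents do not support that: they show an ambiguity between sentences.

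*May* also has a sensible meaning. Items such as memory impairment, emotional withdrawal and motor retardation can belong to the depression under treatment, so not every assessed symptom is an adverse event. That explains the word but does not rescue it, because the pre-existing-condition rule already makes that distinction with a usable criterion.

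The two elicitation instructions could be set against each other, since 12.7.1 says that "the investigator should seek to elicit any clinical or objective reactions by specific questioning". Both are illustrated by a similar open question, so the point does not rest on them.

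Finally, a reader might infer that no structured scale for dissociation is used. That cannot be said. Protocol sections 12.1 to 12.6 and parts of section 9 are not visible, and a scale or a capture criterion may be there. Even so, a scale would not settle what is entered as an adverse event, and the primary endpoint counts adverse events.

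**Conclusion.** The point holds as a minor drafting conflict with a one-directional risk. The quantity exposed is the preferred-term incidence of dissociative events, which could be biased downward and vary by site.

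A reader might carry the halving of the dissociative count over to the primary endpoint. That would hold only if no affected subject had any other adverse event. At 10% affected and 50% recorded, the primary loss is 2.5 subjects per 100 if half have another event and 0.5 if 90% do. The SAP's visit windows run to Day 1820, so another event is likely for many subjects. With repeated dosing, a subject is lost only if every episode goes unrecorded. Both push the primary loss toward the low end. All the rates, and independence, are assumptions.

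A reader might also call dissociation the class effect of most concern for rapastinel. The documents attribute these effects to two NMDA receptor antagonists and describe rapastinel as a glycine-site functional partial agonist. The wording of 12.7 loosely groups it with antagonists but does not rank the concern.

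**What to change.** In protocol section 12.7, replace the permissive clause with a statement that any listed symptom that is new, or worse in frequency, intensity or character than before first dose, will be recorded as an adverse event, subject to the rule in 12.7.1 that related signs and symptoms are grouped as one diagnosis. The reference to grouping matters: without it, one episode with several listed symptoms could be entered as several events.

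The cost is one sentence and a line of site guidance. Staff already make the assessment, and the SAP tables need no change. The downside is a slightly higher recorded adverse event rate. If the change is made while the study is running, the report should give the date it took effect, because records before and after would not be fully comparable.

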12.7.1 Recording of Adverse Events

Subjects should be instructed to report all AEs to the investigator. AE collection begins at signing of ICF and ends 30 days after last dosing injection. In addition, the investigator should seek to elicit any clinical or objective reactions by specific questioning (eg, "How have you been feeling?") and, as appropriate, by examination. Information on all AEs should be recorded on the eCRF. All clearly related signs, symptoms, and results of diagnostic procedures performed because of an AE should be grouped together and recorded as a single diagnosis. The component parts of the diagnosis may be listed for verification. If the AE is a laboratory abnormality that is part of a clinical condition or syndrome, it should be recorded as the syndrome or diagnosis rather than the individual laboratory abnormality.

To avoid vague, ambiguous, or colloquial expressions, all AEs should be recorded in standard medical terminology on the eCRF and on the medical record rather than in the subject's own words. Each AE will also be described in terms of duration (start and stop date), severity, association with the study drug, action(s) taken, and outcome.

